5.1.4 Inclusion criteria for realist interviews

Practice staff

 Any member of staff identified by the practice who have specific ideas and explanations of mechanisms enhancing continuity and how they are implemented or have evolved.

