3.2.3 Realist qualitative interviews

We will interview 3-4 staff members at each practice. We will interview individuals in the practices who understand the processes and programme to enhance continuity, and how they were implemented or have evolved, and who have specific ideas and explanations of the mechanisms that make the programme work, and will likely include GPs, receptionists or practice management.

Realist interviews are theory-driven interviews, and will be conducted by the post-doctoral researcher. The interviews will involve presenting the IPT to participants and eliciting their views on whether from their experiences, they support, reject or suggest modifying the programme theory. (22, 23) Questions will be designed to test the programme theories whilst exploring unexpected and not previously hypothesised CMOcs (theory gleaning as well as theory refinement). Interviews will be conducted face-to-face, audio-recorded and transcribed verbatim.

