5. SAMPLE AND RECRUITMENT

5.1 Stage 2 - Realist evaluation

5.1.1 Sampling

Four general practice sites for participation in the realist evaluation site work will be recruited through collaboration with the South West Research Delivery Network. We will target practices known to the research team to have high levels of continuity through systems including GP personal lists, multi-disciplinary micro-teams, or buddy groups. We will include practices across:

- Urban, rural and costal geographical contexts
- A variety of socio-economic locations, including areas of significant deprivation and those which are least deprived.

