5.1.3 Size of sample for realist interviews

We will interview 3-4 staff members in each practice to a total sample size of 12-16 realist interviews. We will ask the practice to identify members of staff who have specific ideas and explanations of mechanisms enhancing continuity and how they are implemented or have evolved. We envisage that this will involve speaking to GPs, receptionists, and practice management staff.

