5.1.5 Recruitment

The South West Research Delivery Network (RDN) will support the recruitment of GP practices sites. A Research Information Sheet for Practices (RISP) will be developed by the research team to support with the initial recruitment of practice sites.

After initial engagement via the RDN, the RDN will e-introduce a named contact within the practice to the research team. The researcher will contact the practice to further explain the study aims and what is required from the practice, including:

- Identification of practice staff for interviews
- Explaining the ethnographic observational work

Practice participants for realist interviews

The practice study contact will identify potential practice staff for the realist interviews who will be sent an invitation email, with the realist interview participant information sheet.

Practice staff will be invited to speak to the embedded study researcher during the two-week observation period to discuss taking part in the study. The researcher will take verbal consent from the potential participant and the participant will be sent a link to complete the consent form digitally using Microsoft Forms. The mode of interview (face-to face/online) and location, if applicable, will be chosen by the participant. The participant may choose to conduct the interview online after the two week observation period at the practice has ended.

The practice study contact will telephone or email potential GP/clinical pharmacist participants who have not made contact with the research team within 5 days of receiving the original email about the study. This contact is to remind potential participants about the study and provide them with an opportunity to take part in the research during the two week observation period.

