Some staff may feel uneasy or self-conscious about being observed in their work environment. We will address this by providing clear and ongoing opportunities to opt out. Members of staff can either speak to the practice management or the embedded researcher to request that they are not observed at work. The researcher will end any observations if the staff members are showing any signs of discomfort.

Confidentiality of informal conversations

Informal conversations may include sensitive information or identifiable content about patients or colleagues. There is a risk of accidental disclosure. To mitigate this, the researcher will avoid recording identifiable information and will not record sensitive content.

Perceived pressure to participate

Staff may feel pressure to engage with the researcher due to practice-level approval or professional hierarchies. This is addressed through a clear explanation that participation is voluntary and that opting out will not affect their role or relationships within the practice.

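### The only route into the Stage 2 interviews is nomination for ideas on what enhances continuity, and the reminder omits two of the three staff groups expected

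*Protocol*

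**What the plan says.** **Who may be interviewed.** Protocol 5.1.4 (inclusion) admits "Any member of staff identified by the practice who have specific ideas and explanations of mechanisms enhancing continuity"; the sentence goes on to cover how those mechanisms were put in place and have changed. Section 5.1.3 gives the task to the site: "We will ask the practice to identify members of staff who have specific ideas and explanations of mechanisms enhancing continuity". Section 3.2.3 is similar: it looks for people who understand the processes and can explain why the programme works. In 5.1.5 the practice study contact names the staff, who are then invited. No other route to a Stage 2 interview is described. There are no exclusion criteria and no quota by role.

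**How many.** "We will interview 3-4 staff members in each practice to a total sample size of 12-16 realist interviews", from four practices (5.1.1).

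**What the interviews are for.** Under 3.2.3 the initial theory is put to participants to learn whether "they support, reject or suggest modifying the programme theory". Under 3.2.5 the final theory must account for how continuity is supported and also how it is challenged.

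**Which roles are expected.** "We envisage that this will involve speaking to GPs, receptionists, and practice management staff" (5.1.3).

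**Who is reminded.** "The practice study contact will telephone or email potential GP/clinical pharmacist participants who have not made contact with the research team within 5 days" of the invitation (5.1.5). No reminder is stated for anyone else.

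**The concern.** There are two separate issues.

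1. **Selection wording.** The interviews have to be able to produce evidence against the theory, but the nomination request mentions only mechanisms that help. A practice contact who follows it literally will think of the people who can explain why the system succeeds. Someone whose knowledge is mainly of where it breaks down, or for which patients, is not clearly asked for. The sites are themselves chosen for high continuity (5.1.1), so dissent within a site is one of the few sources of contrary evidence. With 3-4 interviews per site, a mild steer can leave a practice with no such account.

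2. **Reminder wording.** Receptionists and managers are expected interviewees, and booking and triage are largely reception work, yet staff in these roles who do not respond are not followed up. Clinical pharmacists, whom 5.1.3 does not list, are. The composition of a small sample may then depend on who was reminded.

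**Working it through.** There is no power calculation or hypothesis test here. The check is one multiplication, a comparison of sections and an illustration.

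**Step 1: the stated total.** Inputs: 4 practices (5.1.1) and 3-4 interviews each (5.1.3). 4 x 3 = 12 and 4 x 4 = 16, which reproduces the stated 12-16. All of them enter by practice nomination.

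**Step 2: selection against purpose.**

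| Section | Content | Direction |
|---|---|---|
| 5.1.3, 5.1.4 | nominated for ideas on mechanisms that enhance continuity | positive only |
| 3.2.3 (selection) | can explain why the programme works | positive only |
| 3.2.3 (purpose) | may back, change or reject the theory | both |
| 3.2.5 (final theory) | continuity supported or challenged | both |

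The purpose runs both ways and the selection wording one way. This is a mismatch of emphasis and not a formal exclusion.

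**Step 3: reminder against expected roles.**

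| Role | Expected (5.1.3) | Reminded (5.1.5) |
|---|---|---|
| GP | yes | yes |
| Receptionist | yes | no |
| Practice management | yes | no |
| Clinical pharmacist | not listed | yes |

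Two of the three expected groups receive no reminder.

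**Step 4: illustration of sensitivity.** The protocol gives no share of staff who would offer a disconfirming account, so the share s is purely an assumption. Treating interviewees as independent, the chance of at least one such account among n is 1 - (1 - s)^n.

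| Assumed s | n = 3 | n = 4 | n = 12 | n = 16 |
|---|---|---|---|---|
| 30% | 66% | 76% | 99% | >99% |
| 20% | 49% | 59% | 93% | 97% |
| 10% | 27% | 34% | 72% | 81% |
| 5% | 14% | 19% | 46% | 56% |

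For example, at s = 20% and n = 3: 1 - 0.8^3 = 1 - 0.512 = 0.488. If nomination lowered the share from 20% to 5%, the chance within one practice would fall from 49-59% to 14-19%, and over all practices from 93-97% to 46-56%. This shows how sensitive so small a sample is to a steer in nomination. It does not estimate the steer.

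**The case against.** The strongest reply is that the rule selects on knowledge and not on support. It extends to how mechanisms were implemented and have evolved, 3.2.3 asks for people who understand the processes, and there are no exclusion criteria. A receptionist who can explain where the system fails could be nominated. Choosing informed insiders is deliberate in theory-driven interviewing. This stands, and it rules out some stronger readings:

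- *A reader might infer that the plan admits only champions.* It does not. That is a likely direction of bias and not a stated rule.
- *A reader might infer that confirmation bias is built into the whole test of the theory.* The interviews are one source among several. Observation is analysed for how it challenges as well as fits the theory (3.2.1). Documents are triangulated with the other data (3.2.2). Coding is partly inductive, and a pause after two practices allows refocusing (3.2.5). Workarounds are among the topics of the walk-throughs (5.1.2). None of this changes who is eligible for interview.
- *A reader might infer that the reminder also favours supporters.* It reaches people already nominated, so it can shift the role mix but cannot select by opinion.
- *A reader might put a size on the role effect.* If half respond at once and half of those reminded then respond, clinicians reach 0.5 + 0.5 x 0.5 = 75% and others stay at 50%. Those rates are assumed. The number invited is not stated and the target is completed interviews, so they do not translate into sample composition.

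Receptionists and managers can also approach the researcher during the two weeks on site (5.1.5), and reception staff are observed (5.1.2). The list of roles in 5.1.3 is an expectation, so including a pharmacist does not contradict it. These points limit the consequence. They do not explain why the other invited staff should go without a reminder.

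On voluntariness, 6.1 recognises that "Staff may feel pressure to engage with the researcher due to practice-level approval or professional hierarchies" and answers it by making clear that participation is voluntary and that opting out carries no penalty. The documents do not show that the reminder has to move to the research team.

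**Conclusion.** The point holds in a limited form. The sole entry rule for all 12-16 Stage 2 interviews is worded in one direction, while the interviews and the final theory must deal with both. This is likely, but not certain, to reduce disconfirming accounts in the interviews, with other data sources as a partial counterweight. The inference assumes that practice contacts follow the wording they are given. The reminder omits two of the three expected staff groups and may tilt the role mix towards clinicians. Neither effect can be measured from the document, and the stated sample size is unaffected. Stage 1 exploratory interviews (3.1) draw on the stakeholder groups and are outside this point. Both wordings are worth correcting before recruitment because they bear on who is interviewed and cost very little to change.

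**What to change.** 1. In 5.1.3 and 5.1.4 (inclusion), refer to mechanisms *enhancing or hindering* continuity. In 3.2.3, make the matching change so that explanations of why the programme does not work are also sought.
2. In 5.1.5, send the reminder to all invited staff in place of GPs and clinical pharmacists only.

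**Cost.** The change is to wording, and the number of interviews stays at 3-4 per site. A few more reminders are sent. Because the practice contact sends them and 6.1 names hierarchy as a source of pressure, the text should repeat that taking part is voluntary. Any invitation text or information sheet that repeats the criterion needs the same edit.

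**Optional.** Let the researcher also invite staff met during observation, within the same 3-4 interviews. If this were one per site, it would be 4 of 16 to 4 of 12 interviews, or 25-33%. The downside is fewer practice-nominated interviewees and extra care over confidentiality, since a known doubter may be recognisable in so small a group. The main fix does not depend on this.

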5.1.4 Exclusion criteria for realist interviews

Practice staff

No specific exclusion criteria

5.1.5 Recruitment

The South West Research Delivery Network (RDN) will support the recruitment of GP practices sites. A Research Information Sheet for Practices (RISP) will be developed by the research team to support with the initial recruitment of practice sites.

After initial engagement via the RDN, the RDN will e-introduce a named contact within the practice to the research team. The researcher will contact the practice to further explain the study aims and what is required from the practice, including:

- Identification of practice staff for interviews
- Explaining the ethnographic observational work

Practice participants for realist interviews

The practice study contact will identify potential practice staff for the realist interviews who will be sent an invitation email, with the realist interview participant information sheet.

Practice staff will be invited to speak to the embedded study researcher during the two-week observation period to discuss taking part in the study. The researcher will take verbal consent from the potential participant and the participant will be sent a link to complete the consent form digitally using Microsoft Forms. The mode of interview (face-to face/online) and location, if applicable, will be chosen by the participant. The participant may choose to conduct the interview online after the two week observation period at the practice has ended.

The practice study contact will telephone or email potential GP/clinical pharmacist participants who have not made contact with the research team within 5 days of receiving the original email about the study. This contact is to remind potential participants about the study and provide them with an opportunity to take part in the research during the two week observation period.

5.1.6 Ethnographic observation: Observations and Informal Conversations

As part of this study, an embedded researcher will conduct non-participant observations and informal conversations with practice staff in order to understand team roles, routines, and workflows that support continuity of care in general practice. These activities will focus on staff practices and interprofessional collaboration; no clinician–patient consultations will be observed, and no patient-identifiable information will be recorded.

Publicising the study to staff

Before fieldwork begins, we will ensure that all staff at participating practices are aware of the study. This will include:

- A brief presentation at a team or practice meeting (coordinated with the practice study contact and management)
- Printed information sheets and posters made available in shared staff areas
- Emails sent by the practice manager or study team introducing the researcher, explaining the aims and nature of the observations, and outlining how staff can opt out

Consent and right to opt out of observations

Because ethnographic research involves immersion in real-world settings where obtaining written consent from every individual in every interaction may not be practical, we will adopt a tiered and ongoing permission process:

- Each participating practice will provide permission for the researcher to be present and observe day-to-day activities. This does not replace individual staff members' rights to opt out, which will be respected at all times.
- Individual staff members will be given clear opportunities to opt out of being observed or engaging in informal conversations. This includes:
 - o Directly informing the researcher
 - o Speaking to the practice manager or study lead, who can relay the message
 - Using a designated email address to contact the study team

The researcher will make themselves known to staff at each visit and will check in regularly to ensure ongoing comfort with their presence. Signs will also be posted in shared areas indicating when observation is taking place.

If a staff member appears uncomfortable, or asks not to be included, the researcher will respectfully step away and no notes will be taken about that interaction.

Informal Conversations

Informal conversations may arise naturally during the researcher's time in the practice. These will not be recorded but may be noted in fieldnotes if relevant to the research question. If a conversation moves into a sensitive area or the participant shares identifiable information about patients or colleagues, the researcher will not record this information and will remind the staff member that participation is voluntary.

Where specific insights from informal conversations are particularly relevant, the researcher may follow up with the staff member to obtain verbal confirmation that the information may be noted and used anonymously in analysis.

6. ETHICAL AND REGULATORY CONSIDERATIONS

6.1 Potential risks

Over the course of the study, we will work to align methodologies and conduct to the UK Policy for health and social care research, in order to protect members of the public and professionals involved in the research. A number of potential risks have been identified, which will require appropriate management and mitigation:

Data Management

A secure chain of data handling from the point of collection at research sites to being received, processed and stored by the research team at the University of Exeter will be in place to ensure that interview recordings are handled and stored in an appropriate manner. Field recordings will be taken using an encrypted audio recorder or through a secure University of Exeter Teams account (for remote interviews. The data extracted from realist interview audio recordings will be stored on a dedicated, secure, restricted access University of Exeter SharePoint site for the duration of the study, which only the research team and data custodian will have access to. Interview recordings will only be stored for up to 90 days after recording to allow anonymised transcriptions to be made using Microsoft Word or Microsoft Teams auto-transcibe. After this period, the recorded interview files will be deleted.

• Time incumbency

Given the current pressures and demands on the health system in the UK, we acknowledge that an hour-long interview is not an insignificant time commitment for GPs and practice-based staff. The research team will make every effort to ensure that interviews take place at a time that is convenient to participants and do not impinge on daily clinical practice or work. The $\mathfrak{L}50$ incentive for professional participants recognises the time commitment made by participants to contribute to this research study.

Unintended inclusion of practice staff

As the researcher will be present in the day-to-day setting of the practice, there is a risk that individuals may be observed or included in fieldnotes without fully understanding that they are part of a research study. This is mitigated by practice posters, emails from practice management to all staff, regular researcher check-ins, and multiple, accessible opt-out routes.

• Discomfort with being observed

Some staff may feel uneasy or self-conscious about being observed in their work environment. We will address this by providing clear and ongoing opportunities to opt out. Members of staff can either speak to the practice management or the embedded researcher to request that they are not observed at work. The researcher will end any observations if the staff members are showing any signs of discomfort.

Confidentiality of informal conversations

Informal conversations may include sensitive information or identifiable content about patients or colleagues. There is a risk of accidental disclosure. To mitigate this, the researcher will avoid recording identifiable information and will not record sensitive content.

Perceived pressure to participate

Staff may feel pressure to engage with the researcher due to practice-level approval or professional hierarchies. This is addressed through a clear explanation that participation is voluntary and that opting out will not affect their role or relationships within the practice.

6.2 Research Ethics Committee (REC) and other regulatory review

Health Research Authority (HRA) approval will be sought before the commencement of the practice recruitment or any general practice based research detailed in this protocol. As part of this approval process, a favourable NHS Research Ethics Committee (REC) decision will need to be in place. The participant information sheets, consent forms, topic guides and other relevant documents will be submitted for review as part of this process. All correspondence with the REC will be retained for information. The REC will be informed when the study ends.

Regulatory Review & Compliance

The Chief Investigator (CI) will ensure that appropriate approvals and confirmations are in place with the participating general practices before sites commence enrolment of practice staff into the proposed research. Specific arrangements on how to gain approval from participating organisations will be in place and comply with the relevant guidance for NHS sites. For any amendment to the study, the CI, in agreement with the sponsor, will submit information to the appropriate body in order for them to issue approval for the amendment. The CI or research post-doctoral fellow will work with sites (both the NHS sites and the research team based at the University of Exeter) to put the necessary arrangements in place to implement the amendment to confirm their support for the study as amended.

Amendments

Any proposed substantial or non-substantial amendments to the study will be shared with the HRA and REC for consideration after discussion with the supervisory team and the sponsor. The sponsor will decide whether an amendment is substantial or non-substantial for the purpose of submission to the REC. Once approved, any participating sites, the research team and the project steering committee will be notified of any amendment details. The amendment history will be documented through retention of all documents pertaining to application for amendment and correspondence with the relevant stakeholders (i.e. the sponsor, REC, research sites) over the course of application and implementation of any amendments.

